included in the romiplostim exposure cohort after they receive romiplostim. The patient experience with ITP before romiplostim exposure will be included in the romiplostim unexposed cohort along with that for all adult chronic ITP patients who never receive romiplostim therapy during the study period.

Adult chronic ITP cohorts (romiplostim “Exposed Cohort” and “Unexposed Cohort”) will include adult patients identified as having chronic ITP (incident and prevalent cases identified through both hospital discharge registry and outpatient clinic registry, as described by [Frederiksen and Schmidt, 1999](#)) on or after the starting date, and up to 1 year prior to the ending date. All patients will be followed-up for **at least 1 year and up to 11 years** in either the romiplostim Exposed Cohort or Unexposed Cohort. Incident and recurrent outcomes of interest will be assessed on an annual basis.

All clinical outcomes (eg, thrombotic/thromboembolic events, hematological malignancies, and other potential outcomes of interest) will be identified by International Classification of Diseases – 10th Revision (ICD-10) codes from the NHRS databases (eg, hospital discharge registry, outpatient clinic registry, pathology registry, death registry, cancer registry, birth registry, and prescription registry) or by review of electronic medical records and/or paper medical charts. As needed, suspected and identified cases will be medically confirmed by review of electronic medical records and/or paper medical charts, laboratory test results, BM biopsy reports, pathology data, pharmacy data, and other relevant health records. Laboratory data will be used to determine thrombocytosis and worsened thrombocytopenia after cessation of romiplostim.

Because ITP is a diagnosis of exclusion and secondary causes of thrombocytopenia may be difficult to diagnose, some patients will require review of medical records and laboratory data including bone marrow exams, if any, prior to their first diagnosis of ITP (ICD-10: D69.3-D69.4). These will include the relevant time periods prior to their first diagnosis of ITP for all patients who have a history of any condition from [Appendix 2](#) prior to the first diagnosis of ITP.

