1.2 Secondary Objectives

Potential clinical risks:

- To describe the phenomenon of worsened thrombocytopenia (platelet count significantly reduced to, or below, baseline platelet count levels) after romiplostim cessation among adult chronic ITP patients
- To study the incidence rate of thrombocytosis (platelet count $> 450 \times 10^9/L$) among romiplostim-treated adult chronic ITP patients with/without adverse events
- To describe the incidence rate of thrombotic/thromboembolic events and the distribution of specific diagnoses of these thrombotic/thromboembolic events for a romiplostim-exposed cohort and an unexposed cohort
- To assess the incidence rate of hematological malignancies and pre-malignant states (focused on acute myelogenous leukemia [AML] and myelodysplastic syndromes [MDS]) for a romiplostim-exposed cohort and an unexposed cohort
- To describe clinically significant bleeding and/or receipt of rescue medication (any new ITP medication prescribed to a chronic ITP patient during romiplostim therapy) in predefined romiplostim therapy periods ([Section 7.1](#))
- To describe the incidence rate of concurrent leukocytosis and anemia (measured by laboratory test results taken within 4 weeks of each other)

³ Clinical signs: any of the following: splenomegaly, hepatomegaly, leukocytosis, and cytopenia

- To describe patient safety profiles, including the incidence rate of renal failure among adult chronic ITP patients with renal impairment medical condition when romiplostim therapy is initiated
- To measure the impact of the EU dosing rule in the cohort of romiplostim exposed patients

Potential BM abnormal findings:

- To describe the prevalence of reticulin and collagen fiber content in the first BM biopsy of adult chronic ITP patients prior to romiplostim exposure, by splenectomy status
- To assess the incidence of collagen fibrosis with associated clinical signs confirmed by findings in BM biopsies of adults with chronic ITP either receiving or not receiving romiplostim
- To study the incidence of chronic idiopathic myelofibrosis (CIMF, primary myelofibrosis) according to the WHO diagnostic criteria in adults with chronic ITP either receiving or not receiving romiplostim

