3.4 Selection of Participants (or Subject Eligibility)

3.4.1 Inclusion Criteria

Subjects in the NCPRR will be those whose health information is recorded by the NHRS of Denmark, Norway, or Sweden.

The eligible adult cITP romiplostim-exposed patients for the NCPRR must meet all of the following criteria:

- Patients must be 18 years or older at the time of chronic ITP diagnosis,
- Patients will have romiplostim therapy between 01 January 2009 and 31 December 2018, and
- Patients will have at least 6 months of medical information prior to initial date of receiving romiplostim treatment (Index Date), data from which will establish a baseline of study subjects.

The eligible adult cITP romiplostim-unexposed patients for the NCPRR must meet all following criteria:

- Patients must be 18 years or older at the time of chronic ITP diagnosis,
- Patients will not have received romiplostim therapy prior to or during the study period between 01 January 2009 and 31 December 2019, and
- Patients will have at least 6 months of medical information in the study period. The data from this period will establish baseline of subjects in the comparison group.

Eligible romiplostim-unexposed cITP patients will be the source of comparison cohorts for romiplostim-exposed cITP patients. Because potential confounding factors (eg, severity of ITP condition) may cause some biases for the study, however, robust propensity scoring and adjusted analyses will be essential ([Section 12](#)). In addition, appropriate contextualization from other recognized data sources will be used in comparisons to address selection biases.

In addition, according to initial dates of receiving romiplostim therapy among patients in the Exposed Cohort, the follow-up time period will be separated into 2 periods: (1) follow-up time period prior to romiplostim exposure, and (2) follow-up time period following romiplostim exposure. Patient experiences in the follow-up time period prior to the initial date of receiving romiplostim therapy will be considered as another “within-patient” comparison with the patient experiences during the follow-up time period after the initial date of receiving romiplostim therapy.

Eligible romiplostim Off-Label-Exposed patients will be any patient who received romiplostim therapy without an adult chronic ITP diagnosis.

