5.4 Ascertainment for Laboratory Data Outcomes

The effect of romiplostim on thrombocytosis and worsened thrombocytopenia after cessation of romiplostim therapy will be assessed based upon laboratory data. The NHRS contains all laboratory testing results. The study will review all electronic laboratory results through 4 predefined romiplostim study time periods. Two types of data will be obtained: 1) average level of platelet counts for each predefined time period; and 2) frequency of platelet counts above or below the normal range for each predefined time period. Thrombocytosis will also be confirmed by electronic medical chart review, and will be assessed whether it occurs with an adverse experience or not. In addition, rescue medication data for thrombocytopenia will also be obtained, and will be used to adjust for treatment effects in different study periods.

5.5 Standard Review of BM Biopsies and Related Study Plan for Patients with BM Biopsy

BM biopsy-related secondary endpoints of the NCPRR will be based upon all ITP patients who have at least 1 BM biopsy stained for reticulin and collagen registered in the National Pathology Registry (SNOMED: T06000, T06001, T06002 and/or S45410). For the purpose of NCPRR BM study requirements, all BM specimens for adult chronic ITP patients will be requested to be stained for reticulin and collagen.

To ensure these standards, 2 pathologists will independently re-review all BM biopsy specimens. If diagnostic conclusions for a BM biopsy from both pathologists are inconsistent, a third pathologist will re-review the specimen to achieve a final diagnosis. All reviews will be blinded to romiplostim treatment status.

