7. REGISTRY FOLLOW-UP PERIOD, EXPOSURE TIME, AND TIME AT RISK FROM EXPOSURE

7.1 Registry Follow-up Period

The follow-up period will be separated into 4 periods:

- Six months prior to receiving romiplostim therapy: This period is considered a cohort qualification and baseline establishment period. Using this period, the eligibility of subjects will be challenged and confirmed, disease conditions will be assessed, and propensity scores will be assigned for each patient. Based on the information, study cohorts will be established.

- Under treatment period: The period is defined as being from Index Date to 10 days after the last dose of romiplostim medication. During this period, all study outcomes will be assessed except for outcomes related to latency effects and post treatment effects.
- Period immediately after romiplostim treatment cessation: This period is defined as between 10 to 100 days after the last dosing. The period will be used to assess risk of worsened thrombocytopenia after treatment cessation (eg, platelet counts, bleeding, as well as rescue medication usage). As needed, this study will separate this time period into 2 sub-time periods: (3a) time period from 10 to 30 days after the last dose; and (3b) time period from 30 days to 100 days after the last dose.
- Post treatment period: This is defined as the period from 100 days after the last dosing to the end of the study. This period, as well as the aforementioned 3 periods, will be used to study long term effects of romiplostim (eg, malignancies).

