7.2 Exposure Time

Exposure time is defined as the period the patient is receiving romiplostim therapy. A patient will be considered to be on “maintenance” therapy when the patient receives the same dose of romiplostim for 4 subsequent weeks.

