12.4 Analysis for Long-term Effects

Analysis for long-term effects will be descriptive in nature. As the selection bias resulting from confounding by indication for this study could be very large, and as some impacts are not measurable, comparative analyses will be inherently challenging to interpret. For these reasons any comparative analyses must be considered as exploratory for signal detection and for the purpose of hypothesis generation. The incidence rates of clinically significant bleeding (inpatient and outpatient) and/or rescue medication use will be described for the Exposed Cohort and Unexposed Cohort:

- Kaplan-Meier survival curves will be constructed for patients with bleeding events for the Exposed Cohort and Unexposed Cohort.
- As needed, a Cox model with romiplostim exposure as a time-varying covariate will be used to compare the total event-free survival rates among exposed ITP patients and the unexposed cohort, with an estimation of the relative risk and associated 95% confidence interval. This analysis will adjust for potential confounders and propensity scores. Stratification by propensity score, significant year spans, and country may be considered for this analysis, although such an analysis will only be for exploratory and hypothesis generating purposes. Other treatment exposures,

health status, and disease conditions may also be considered for inclusion in the model as time-varying covariates.

Comparison of platelet counts in predefined time periods (prior to, during, immediately after treatment cessation, and post treatment) between the Exposed Cohort and Unexposed Cohort:

- Mean and SD
- As needed, a multiple regression will be used to test the difference between the Exposed Cohort and Unexposed Cohort. However, such an analysis will only be for exploratory and hypothesis-generating purposes.

Comparison of long-term safety (eg, thromboembolic risk, thrombocytosis, hematological malignancies, focused upon AML, and MDS), including:

- Description of rare and long latency events: Some events (eg, AML and MDS) are too few to conduct any meaningful statistical analysis or comparison. The study will provide detailed case descriptions for each case observed.
- Incidence rate of these events will be calculated.

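### Rescue medication is defined only for time on romiplostim, yet the protocol plans rescue rates for unexposed patients and rescue assessment after cessation

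*Protocol*

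**What the plan says.** One secondary objective, worded identically in the synopsis and in Section 1.2, is to describe clinically significant bleeding and/or receipt of rescue medication. Rescue medication is explained there in parentheses as "any new ITP medication prescribed to a chronic ITP patient during romiplostim therapy". The glossary has no entry for the term, and no other section defines it.

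Later sections use the term as follows:

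- **Section 12.4** covers incidence rates in both cohorts: bleeding and/or "rescue medication use will be described for the Exposed Cohort and Unexposed Cohort".
- **Section 7.1** gives the window from 10 to 100 days after the last dose the purpose to "assess risk of worsened thrombocytopenia after treatment cessation (eg, platelet counts, bleeding, as well as rescue medication usage".
- **Section 6.2** and the synopsis endpoint list ask for bleeding and/or rescue receipt in each predefined Section 7.1 period, without limiting rescue to time on the drug.

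Two further statements fix who is on therapy and when. Section 7.2 says "Exposure time is defined as the period the patient is receiving romiplostim therapy". Section 3.4.1 requires of unexposed patients: "Patients will not have received romiplostim therapy prior to or during the study period between 01 January 2009 and 31 December 2019". The synopsis study design adds: "The patient experience with ITP before romiplostim exposure will be included in the romiplostim unexposed cohort".

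**The concern.** A definition tied to being on romiplostim cannot be used in people, or in time, without romiplostim. If the definition were applied as written, no event in the Unexposed Cohort could qualify as rescue, and neither could a drug started in the cessation window. The exposed and unexposed rescue rates would then not describe the same thing.

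The cessation window matters in its own right. Section 2.3 lists transient worsening of thrombocytopenia after stopping treatment among the key risks in the Risk Management Plan, and rescue use is one of the signs that Section 7.1 names for assessing it.

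If the definition is instead set aside, nothing in the protocol says what counts as new in a patient who never started romiplostim, or against which reference period. Annual analyses in three countries could then settle this differently.

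**Working it through.** No arithmetic applies, because the protocol gives no rescue or bleeding rates. The check is to hold the definition against each kind of patient time in which rescue is to be reported.

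| Patient time | Source | On romiplostim? | Rescue to be reported? | Can the definition be met? |
|---|---|---|---|---|
| Never-exposed patients | Sections 3.4.1, 12.4 | No | Yes | No |
| Time before the first dose, counted as unexposed | Synopsis, Sections 3.1, 12.4 | No | Yes | No |
| Index Date to 10 days after the last dose | Sections 7.1, 6.2 | Yes | Yes | Yes |
| 10 to 100 days after the last dose | Sections 7.1, 6.2 | No | Yes, named explicitly | Not as worded |
| More than 100 days after the last dose | Sections 7.1, 6.2 | No | Yes, through the endpoint | Not as worded |

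1. **Unexposed time.** Never-exposed patients have no romiplostim before or during the study period. Time before a later first dose also contains none. No reading of the phrase, however loose, makes either of them time during romiplostim therapy. Section 12.4 nevertheless asks for the rate there. This conflict is firm.

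2. **Cessation window.** Section 7.1 ends the treatment period 10 days after the last dose and opens a separate window of 100 − 10 = 90 days. Section 7.2 ties exposure time to receiving the drug. Rescue in this window is therefore outside the definition as worded, although Section 7.1 names it as something to assess.

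3. **The objective itself.** The sentence that contains the definition goes on to report the outcome by the Section 7.1 periods, and these extend past the end of treatment. The limit and the reporting frame disagree within one sentence.

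4. **Intended meaning.** The endpoint text, Section 7.1 and Section 12.4 all point to a wider meaning. The conflict therefore lies between a narrow definition and broader planned uses. The protocol does not plan a zero count.

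**The case against.** The best defence concerns time after cessation. The protocol uses its romiplostim therapy or treatment periods as a label for all the Section 7.1 periods. The parenthetical could be shorthand for them, and an analyst following Sections 6.2 and 7.1 would count rescue after cessation. This has force and makes that half of the point the weaker one, although the wording still disagrees. It does not help with the Unexposed Cohort.

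A second defence is that operational detail belongs in the statistical analysis plan. That is true of drug lists and codes. Here, however, the protocol states a definition and also plans analyses that the definition cannot serve, so an analysis plan would have to depart from one or the other.

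Three stronger readings are tempting and are not supported:

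- **That the comparison is biased against romiplostim.** This follows only if the parenthetical overrides Sections 6.2, 7.1 and 12.4, which the text as a whole does not suggest. Counting how many periods fall outside the definition measures no effect.
- **That Section 5.4 is a further contradiction.** It says that "rescue medication data for thrombocytopenia will also be obtained, and will be used to adjust for treatment effects in different study periods". That is use as an adjustment variable for platelet analyses, and it need not follow the definition of an outcome.
- **That bleeding and rescue must be reported separately.** The and/or wording already permits this, so it is a preference and no correction.

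**Conclusion.** The point holds as a minor inconsistency. The sole definition of rescue medication cannot apply to the Unexposed Cohort, for which Section 12.4 plans rates, and as worded it conflicts with the post-cessation assessment in Section 7.1. The first part is certain. The second depends on reading the phrase in its ordinary sense, with Sections 7.1 and 7.2 separating treatment from cessation.

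The reach is small. The outcome is secondary and descriptive, and comparisons are declared exploratory. The Kaplan-Meier curves in Section 12.4 cover bleeding only, and the primary bone marrow outcome is untouched. Neither the size nor the direction of any bias can be derived from the protocol. The conclusion assumes only that no definition exists in this document beyond the objective's parenthetical. A separate analysis plan may hold a workable one, but the protocol would still need to agree with it.

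**What to change.** Delete the limit to romiplostim therapy from the objective in the synopsis and Section 1.2. Define rescue medication as the start of an ITP medication other than romiplostim, or escalation of one already in use, after the Index Date of Section 4.1 and judged against the six months before that date. Apply the rule identically to unexposed time and to every exposed Section 7.1 period after the Index Date.

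Three details matter:

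- **Escalation has to count.** Chronic ITP is defined partly by continual treatment, so a rule limited to drugs not in use at baseline would miss stepped-up doses.
- **The reference period should be the six months before the Index Date.** For unexposed patients Section 3.4.1 takes six months inside the study period and says "The data from this period will establish baseline of subjects in the comparison group". That stretch can fall after the Section 4.1 Index Date, so it would not give the two cohorts the same starting point.
- **Two dates need a clarifying line.** Section 4.1 imputes an Index Date only for never-exposed patients, so the same imputation should start the clock for the pre-romiplostim time of patients treated later. It should also say whether the diagnosis date means first ITP or chronic ITP. If it means first ITP, initial treatment would be counted as rescue.

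The cost is a reworded definition and a consistent medication look-back. Section 12.3 already uses six months of data before an index date in both cohorts and lists prior ITP medications among the variables to consider. The remaining downside is interpretive: a new drug in an unexposed patient, or after romiplostim stops, may be a planned switch and not rescue, so between-cohort rates need cautious reading.

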2. BACKGROUND AND RATIONALE

2.1 Disease and Therapeutic Area

Idiopathic (Immune) thrombocytopenia (ITP) is an autoimmune disorder characterized by platelet destruction caused by antiplatelet autoantibodies, concurrent with evidence of inadequate platelet production by the bone marrow ([McMillan, 1981](#)).

The all-cause mortality rate in adult patients treated for ITP is approximately 4% in 75 months ([Berchtold and McMillan, 1989](#)). All currently available treatments have substantial morbidities that often require discontinuation of treatment.

Thrombocytopenia is resolved in approximately 50% to 75% of patients with ITP after therapy with standard-dose corticosteroids, splenectomy, or both

(Berchtold and McMillan, 1989; Cines and McMillan, 2005). Patients refractory to these treatments may receive other treatments (including pulsed dexamethasone, danazol, colchicine, cyclophosphamide, azathioprine, staphylococcal A immunoadsorption, cyclosporin, anti-immunoglobulin D, or single-agent or combined chemotherapy), but response is generally poor (Berchtold and McMillan, 1989; Cines and McMillan, 2005).

2.2 Romiplostim Therapy for Chronic ITP

Romiplostim is a thrombopoiesis-stimulating protein that targets the thrombopoietin (TPO) receptor. Romiplostim is an Fc fusion protein (peptibody) that increases platelet production through binding and activation of the TPO receptor (also known as c-Mpl), which activates intracellular transcriptional pathways. Romiplostim was initially developed as a treatment for thrombocytopenia associated with adult ITP. Clinical trials in subjects with adult ITP have demonstrated that romiplostim is an effective and safe treatment for ITP. This molecule has the ability to increase platelet counts regardless of splenectomy status.

2.3 Rationale for the NCPRR

Clinical trials have demonstrated that romiplostim is an effective and safe treatment for adult chronic ITP. While romiplostim clinical trials have produced important data about treatment efficacy in controlling ITP, trial data may not fully reflect the diverse population that may receive romiplostim in the post-marketing setting. In addition, since this is an orphan indication, there is inherently some limitation as to the robustness of the long-term safety data. The NCPRR will potentially provide additional real-world data to help address these 2 issues.

The NCPRR will collect data from all romiplostim-treated adult chronic ITP populations in the 3 selected Nordic countries. As a result, data from the NCPRR will be representative of the real-world patient experience. Amgen plans to use the NCPRR as an infrastructure for post-marketing PV to assess the acute and long-term safety of romiplostim therapy. The study will allow Amgen to describe the natural history of the disease and incidence of co-morbidities, and the safety of romiplostim therapy, and will support risk evaluation and mitigation activities.

This registry is part of Amgen's global effort to assess the effects of romiplostim treatment. Amgen will assess observed and potential risks related to romiplostim therapy in the real-world clinical practice setting in this registry and all other pharmacovigilance efforts as listed in Amgen's romiplostim Risk Management Plan (RMP), a global regulatory document that outlines the strategic plan to assess identified

and potential risks of romiplostim. Specifically, the following are some key events noted in the RMP as identified and potential risks based on non-clinical and clinical data:

- Reversible bone marrow fibrosis in animals and increased bone marrow (BM) reticulin in humans. This observation has been identified as a reversible, on-target, expected outcome of stimulation with TPO.
- Transient worsened thrombocytopenia after cessation of treatment has been observed in clinical studies.
- A hypothetical concern regarding hematopoietic growth factors is that they may enhance the growth of existing malignancies or promote the growth of new malignancies that are influenced by the receptor-ligand axis. The TPO receptor is predominantly expressed on cells of the myeloid lineage, and there is no confirmed expression on solid tumors ([Graf et al, 1996](#); [Columbyova et al 1995](#)); therefore, it is not expected that romiplostim will promote the growth of solid tumors. In the ITP clinical program, there is no evidence of increased neoplasia, including hematopoietic malignancies; there is, however, a potential risk that TPO receptor agonists may stimulate the progression of existing hematopoietic malignancies or MDS among patients with thrombocytopenia caused by conditions other than ITP. Ongoing clinical studies in other patient populations, including MDS, will help to assess this potential risk.

Other potential risks include:

- Thrombotic/thromboembolic complications
- Progression of increased reticulin to an irreversible BM fibrotic state

In Europe, the product label includes further dose adjustment rules that have been specified by the European regulator as a risk minimization measure of thromboembolic risk and have not been tested in clinical trials.

Dose adjustment rules as specified in the European label

Platelet count (x 10 ⁹ /L)	Action
<50	Increase once weekly dose by 1 mcg/kg
>150 for 2 consecutive weeks ^a	Decrease once weekly dose by 1 mcg/kg
>250 ^a	Do not administer, continue to assess platelet count weekly After the platelet count has fallen to < 150 x 10 ⁹ /L, resume dosing with once weekly dose reduced by 1 µg/kg

^a Due to the inter-individual variable platelet response, in some patients platelet count may abruptly fall below 50 x 10⁹/L after dose reduction or treatment discontinuation. In these cases, if clinically appropriate, higher cut-off levels of platelet count for dose reduction (200 x 10⁹/L) and treatment interruption (400 x 10⁹/L) may be considered according to medical judgment

To address these identified and potential safety issues, Amgen is committed to establishing a comprehensive risk management program which includes cautionary instructions in the prescribing information, PV (both routine and proactive), risk management activities, and additional clinical studies. Amgen believes these actions are appropriate and adequate to manage and minimize the safety risks of romiplostim. As additional safety data becomes available from ongoing and future clinical studies and post-marketing experience, the identified and potential risks will be re-evaluated, and risk management activities will be adjusted.

The NCPRR is specifically designed to fulfill the above post-market PV requirements by the European regulatory authority. In line with these PV requirements, the study assesses acute and long latency effects of romiplostim in real-life clinical practice in three European countries for 11 years (from 01 January 2009 to 31 December 2019).

The National Health Registry System (NHRS) of Denmark, Sweden, and Norway gather all health-related data on their citizens through a complex system of interlinked databases. The Danish government, for example, has compiled nearly 200 registry databases (some initiated in the 1930s) on various datasets from medical records, hospitalization, prescriptions, laboratory and pathology results, cancer registry, and mortality to socioeconomic data on jobs and salaries. The registry databases are population-based and complete. What makes the databases a prime research tool is the fact that they can all be linked by the 10-digit personal identification number (called CPR) that follows each Danish citizen from birth to death ([Frank, 2000](#)).

Thereby the entire lifetime information of each romiplostim-exposed patient between 01 January 2009 and 31 December 2019 (11 years) can be extracted and analyzed to meet the needs of post-marketing safety surveillance. The National Health Registry databases of the 3 countries have been previously used to determine the safety profile of pharmaceuticals, and are considered to be among the best PV and epidemiology tools by regulatory authorities, epidemiologists, and safety specialists in both the medical and scientific communities.

